#### NEW INDICATIONS OF USE

Regarding the new restrictions, some of these criteria are not directly captured in the databases. Thus, operational definitions are proposed using some proxies which could lead to some misclassification or underestimation of the new restrictions. Therefore, some validation or refinement steps based on data availability and quality are required and will be further discussed with each of the academic partners before data extraction; for instance through feasibility assessed on a random sample.

- *A physician with experience in the treatment of osteoporosis.* The operational definition for this in our data sources will be:
  - Therapy initiation in secondary care settings (where available: Aarhus Database)OR
  - Therapy initiation in primary care by a physician with a “high number” of patients diagnosed with osteoporosis or on anti-osteoporosis treatment under his/her care. As both national regulations and prescribing practices have changed throughout the participating databases in recent months (e.g. general practitioners are not allowed to either initiate or prescribe repeat prescriptions of SR in Italy, different to Spain, where GPs cannot initiate but can issue repeat prescriptions of the drug), the definition of “high number” of patients with a diagnosis or treatment for osteoporosis will be based on national figures: a GP will be classified as “experienced” (with a high number of osteoporotic patients) if the number of patients with a diagnosis or treatment for osteoporosis registered with him/her is above a discriminant threshold; for instance, in the top quartile (percentile 75 or above) in the same country/data source.
- *Initiation of SR therapy not in first line,* will be operationalized as:
  - Previous use of other anti-osteoporosis drugs at any time before SR therapyOR
  - History of any formal contra-indications or precautions for the use of oral bisphosphonates (according to SmPC for alendronic, risedronic and ibandronic acid) not recognised as contra-indications or precautions for the use of SR [Appendix 14.3] at any time before SR therapy.

- Use of SR for the treatment of severe osteoporosis, will be operationalized as:
  - History of a previous osteoporotic fracture [Appendix 14.3.2] (at any time before SR therapy initiation).
- OR
  - High absolute fracture risk, defined as  $\geq 10\%$  5-year fracture risk according to the Garvan prediction tool (Nguyen, 2008) (where data on age and either bone mineral density or weight are available for the estimation of risk).

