**Table (9.4) 1 - Overview of contributing databases**

Country	Netherlands	United Kingdom	Denmark	Italy	Spain
Name of the database	IPCI	THIN	Aarhus	HSD- Thales	SIDIAP
Type of database	MR	MR	ADM	MR	MR
# patients, millions	1.2	3.5	1.8	1.5	5.1
Age categories	All	All	All	>15 years	>15 years
Date in	Yes	Yes	Yes	Yes	Yes
Date out	Yes	Yes	Yes	Yes	Yes
Date death	Yes	Yes	Yes	Yes	Yes
Prescriptions					
Outpatient Rx	Yes (specialist incomplete)	Yes (specialist incomplete)	Yes	Yes (specialist incomplete)	Yes (specialist incomplete)
Coding of drugs	ATC	BNF/Multilex	ATC	ATC	ATC
Dosing regimen	Yes	Yes	No	Yes (incomplete)	Yes
Outcomes					
Hospitalizations	Yes	Yes	Yes	Yes	Yes
Outpatient diagnoses	Yes	Yes	Yes	Yes	Yes
Coding of disease	ICPC	READ	ICD-10	ICD-9 CM	ICD-10
Cause of death	Yes (from text)	If linked to death registry	Yes	No	No

*ADM = administrative; ATC = Anatomical Therapeutic Chemical; BNF = British National Formulary; ICPC = International Classification of Primary Care; MR = Medical Records*

All of the chosen databases comply with European Union (EU) guidelines on the use of medical data for medical research and have been validated for pharmaco-epidemiological research (Cazzola, 2011; Vlug, 1999).

The databases will be THIN (UK), HSD (Italy), IPCI (NL), the Aarhus University Database (DK) and SIDIAP (Spain). Table (9.4) 1 provides an overview of key elements of these databases. The total number of persons in the source population will be around 12 million as of 2012.

HSD (Italy), IPCI (Netherlands), SIDIAP (Spain) and THIN (UK) are listed under the ENCePP resources database: ([www.encepp.eu/encepp/resourcesDatabase.jsp](http://www.encepp.eu/encepp/resourcesDatabase.jsp)).

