**Table (9.5) 1 - Number of SR users in available data sources in 2012**

Country	Data source	Denominator	Incident users			Prevalent users		
			Total	Men	Women	Total	Men	Women
Italy	HSD	1.5 million	1209	80	1129	10129	613	9616
Spain	SIDIAP	5.1 million	4008	383	3625	14502	917	13585
UK	THIN	3.5 million	514	65	449	2563	255	2308
DK	Aarhus	1.8 million	46	5	41	464	42	412
NL	IPCI	1.2 million	42	1	41	106	14	92
TOTAL		13.1 million	5819	534	5285	27764	1841	26013

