### ***New restrictions***

Prevalence of each of the new restrictions for indication will be estimated on a patient level (new and prevalent users of SR) by age, sex, period and country. 95% Confidence Intervals will be estimated using a binomial distribution.

Interrupted time series analyses with segmented linear regression will be carried out to assess the impact of the RMM on these, as described above. Primary outcomes of interest will be proportion of SR users with: 1. A history of previous osteoporotic fracture/s or a “high estimated fracture risk” (as defined above); 2. Therapy initiation by a physician experienced in the treatment of osteoporosis (as defined above). 3. SR use not in first line (as defined above).

These analyses will be conducted separately for prevalent and incident SR users.

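### After the Spanish restriction, the experienced-prescriber outcome in SIDIAP grades a GP who did not start the drug, so that series cannot show a move to specialist initiation

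*Protocol*

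**What the plan says.** Protocol section 9.3.2 (New indications of use) gives two alternative routes to the experienced-physician criterion. The first is "Therapy initiation in secondary care settings (where available: Aarhus Database"); no other database is named. The second is "Therapy initiation in primary care by a physician with a “high number” of patients diagnosed with osteoporosis or on anti-osteoporosis treatment under his/her care". The threshold is to follow national figures, with an example: "for instance, in the top quartile (percentile 75 or above) in the same country/data source".

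The reason given for national figures is that prescribing rules have changed. Italian GPs may neither start nor repeat SR, "different to Spain, where GPs cannot initiate but can issue repeat prescriptions of the drug". No separate route is then given for Spanish patients started outside general practice.

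Section 9.4.5 describes SIDIAP as a database of primary care electronic records. Table (9.4) 1 lists its outpatient prescriptions as "Yes (specialist incomplete"), the same entry as for IPCI, THIN and HSD; Aarhus has an unqualified yes.

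Section 9.7.2.2 (New restrictions) makes "Therapy initiation by a physician experienced in the treatment of osteoporosis (as defined above") one of three primary outcomes for the new restrictions, analysed by segmented regression on monthly proportions.

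**The concern.** The criterion asks who started the drug. In SIDIAP the only working route asks how many osteoporosis patients the GP has. Once Spanish GPs may no longer initiate, the GP being graded is, by the protocol's own account, not the initiator of any permitted new course. A national threshold does not help, because it changes where the cut falls and not which physician is graded.

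The fault lies where the time series looks for its effect. Section 9.3.2 places the rule changes in recent months, and the protocol is dated January 2015. If starts in Spain moved to specialists, the outcome should rise. The stated rule could show no change, or even a fall, in the database with the most SR users.

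**Working it through.** **1. Weight of SIDIAP.** Inputs are from Table (9.5) 1, year 2012.

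- Incident users: 1,209 + 4,008 + 514 + 46 + 42 = 5,819, which reproduces the stated total. SIDIAP share: 4,008 / 5,819 = 68.9%.
- Prevalent users: 10,129 + 14,502 + 2,563 + 464 + 106 = 27,764, also as stated. SIDIAP share: 14,502 / 27,764 = 52.2%.

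SIDIAP is the largest source on both counts.

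**2. Applying the rule to a permitted SIDIAP start after the restriction.** Such a start is made outside general practice and the GP then repeats it. The secondary-care route names only Aarhus, which leaves the primary-care route. It can be read in two ways.

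| Reading of the primary-care route | Result for permitted SIDIAP starts |
|---|---|
| Literal: initiation must occur in primary care | All fail |
| First SR record is graded by the patient's GP | Pass if the GP is above the threshold, otherwise fail |

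On the second reading some patients pass, but for a reason unrelated to who started treatment. Neither reading lets the monthly proportion respond to a move to specialist initiation. The top quartile is only an example, but any threshold on GP patient counts behaves in the same way.

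**3. Size on the second reading.** Let s be the share of Spanish SR starters whose GP is above the threshold. If all permitted starts are specialist starts, the share wrongly failed is 1 − s. The documents do not give s, so it is assumed, using the top-quartile example:

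- Starters spread evenly over GPs: s = 0.25.
- Starters in proportion to GP osteoporosis lists, with lognormal list sizes: s = Φ(σ − 0.674), where σ = √ln(1 + CV²).
  - CV 0.5: σ = 0.472, s = 0.42.
  - CV 1.0: σ = 0.833, s = 0.56.

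The share wrongly failed is therefore 1 − 0.25 = 75% at one end and 1 − 0.56 = 44% at the other. On the literal reading it is 100%.

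**4. What the planned analysis without Spain leaves.** At 2012 counts, 5,819 − 4,008 = 1,811 incident users remain (31.1%). If Italy also contributes none, as section 6 expects for the assessment period, 1,811 − 1,209 = 602 remain (10.3%).

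**The case against.** The strongest reply is that the definition is provisional. Section 9.3.2 warns that the proxies may misclassify or underestimate, and it requires validation or refinement with each partner before extraction. The threshold is an example, and the secondary-care route applies where data allow. SIDIAP's specialist prescriptions are incomplete rather than absent, and section 9.4.5 says that it also holds pharmacy invoicing and specialist referrals, so some specialist starts may be identifiable. Sections 4, 8 and 9.7.5 already plan a sensitivity analysis without Spain.

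Much of this stands. The team foresaw weak proxies, has data that might help, and will show results without Spain. But the caveat is general, while the fact that defeats the rule in SIDIAP is already stated in the same bullet. Removing Spain also leaves the main result and the SIDIAP series uncorrected.

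A reader might go further and infer a large error in the pooled proportion by weighting the SIDIAP error by its 69% share, or by 87% without Italy (4,008 / 4,610). The documents do not support that:

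- Those shares predate the restriction. Section 9.5.2 expects only 500 to 1,000 eligible incident users a year in 2013–2015 across all sources, against 4,008 in SIDIAP alone in 2012. Post-restriction shares are not given.
- Section 9.7.2.2 analyses each database as its own control. Section 9.7.4 pools by meta-analysis, and the analysis of combined individual data is additional.

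A reader might also infer that every specialist-started patient is misclassified. That follows only on the literal reading; on the other, those with an above-threshold GP pass.

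**Conclusion.** The point holds for SIDIAP after the Spanish restriction. As written, the rule either fails every permitted start or sorts starts by a GP who did not make them. The SIDIAP series for this one primary outcome then cannot measure what it is meant to measure.

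The range of 44% to 75% wrongly failed rests on three assumptions: the top-quartile example is used, 25% to 56% of starters have an above-threshold GP, and the restriction is followed. The fault itself needs only the two statements in section 9.3.2. No pooled error can be given, and the other two new-restriction outcomes are not touched by this point.

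**What to change.** Amend section 9.3.2 so that the GP-count rule applies only in sources and months where GPs may initiate SR. That excludes SIDIAP after the date of the Spanish restriction, which the protocol does not give and which must be obtained. It also excludes HSD after December 2013, when section 6 dates the Italian ban.

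For SIDIAP after the restriction, identify specialist initiation from the referral and prescription data described in section 9.4.5, if the planned feasibility sample shows that this works. If it does not, run no time series for this outcome there. Report it descriptively, as determined by national law and not as an effect of the risk minimisation measures.

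Scoring all such starts as meeting the criterion should be at most a labelled sensitivity analysis. It would set the outcome to 100% by assumption and credit a national prescribing law to the measures.

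The cost is one change to a classification rule, one date to obtain, and less data for this outcome in the assessment period.

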### 7.2. Regulatory action

In the frame of 13th PSUR assessment, data submitted raised concern regarding cardiovascular safety beyond the already recognized risk for venous thromboembolism. Analysis of pooled data from randomized studies in around 7,500 post-menopausal women with osteoporosis showed an increased risk of myocardial infarction with Protelos/Osseor as compared with placebo (1.7% versus 1.1 %), with a relative risk of 1.6 (95% CI, 1.07 to 2.38), and an increased risk of venous thrombotic and embolic events — 1.9% versus 1.3 % with a relative risk of 1.5 (95% CI, 1.04 to 2.19).

As a result of this assessment, an increased risk for serious cardiac disorders, including myocardial infarction has been identified and risk minimization measures specifically targeting this identified risk were recommended by the CHMP. These risk minimization measures included a restriction of the target population by excluding patients with established, current or past history of ischaemic heart disease, peripheral arterial disease and/or cerebrovascular disease and/or uncontrolled hypertension, and restricting the indication to severe osteoporosis in postmenopausal women at high risk for fracture to reduce the risk of vertebral and hip fractures and the treatment of severe osteoporosis in adult men at increased risk of fracture. Patients with significant risk factors for cardiovascular events (e.g. hypertension, hyperlipidaemia, diabetes mellitus and smoking) should only be treated with strontium ranelate after careful consideration. In addition, strontium ranelate therapy should only be initiated by a physician with experience in the treatment of osteoporosis. These changes were disseminated in the form of a DHPC in May 2013.

In view of this newly identified risk of serious cardiac disorders, an overall benefit/risk review under Article 20 of regulation (EC) No 726/2004 started in May 2013 and was finalized on 20 February 2014 ([EMA/112925/2014, 2014](#)). This led to a restriction of the indication to patients (postmenopausal women and men) with severe osteoporosis at high risk of fracture for whom treatment with other medicinal products approved for the treatment of osteoporosis is not possible due to, for example, contraindications or intolerance. As part of RMM, a new DHPC was disseminated in March 2014.

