### 9.5.1. RMM effectiveness study

[figure not shown]
Based on published studies, the combined prevalence of MI, CVD and PAD before the DHPC published in May 2013 is assumed to be of 19.2% in female and 29.5% in male new users of SR (Abrahamsen, 2014).

A total of **320** male users of SR will suffice to estimate with a 95% confidence and an absolute precision of  $\pm 0.05$ , an unchanged prevalence of MI/CVD/PAD of 29.5%. Similarly, **239** female SR users would suffice to estimate with a 95% confidence and an absolute precision of  $\pm 0.05$ , an unchanged prevalence of MI/CVD/PAD of 19.2%.

Regarding the prevalence of new indication/restrictions of use (severe osteoporosis, and second line therapy), recent data suggest that the prevalence of these would range from 13.0% (Svanstrom, 2014) to 53.1% (Abrahamsen, 2014) for previous fragility fracture (severe osteoporosis), and from 40.4% (Svanstrom, 2014) to 47.9% (Abrahamsen, 2014) for the use of SR as a second line anti-osteoporosis treatment. Given this, 383 users of SR would suffice to estimate (with 95% confidence and 5% precision) an unchanged prevalence of 53.1% (most conservative scenario) for both indications. Lower numbers would be needed if this prevalence either increases or decreases (See Figure (9.5.1) 1).

A number of scenarios with different possible prevalence rates of MI/CVD/PAD, previous osteoporotic fracture, and use as a second line anti-osteoporosis therapy amongst SR users in subsequent years in the period before the publication of the DHPC in May 2013 (*reference*) and after the publication of the second DHPC from April 2014 onwards (*assessment* period) are presented in Figure (9.5.1) 1.

**Figure (9.5.1) 1 - Number of SR users required to estimate the prevalence of contraindications or new indication/restrictions with a 5% absolute precision**

[figure not shown]
For the interrupted time series analyses (see details below), sample size calculations are related to the estimation of the number of observations or time points at which data will be collected. According to the quality criteria of Ramsey et al, at least 10 pre- and 10 post-intervention data points would be needed to reach at least 80% power to detect a change (if the autocorrelation is  $>0.4$ ) (Ramsay, 2003). Our outcomes will be estimated at monthly intervals to ensure that  $>10$  data points are available for both the pre-defined *reference* and *assessment* analysis periods.

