### Contraindications / precautions of use of oral bisphosphonates (and not mentioned in the SR SmPC)

Term/Description	ICD10	ICD9CM	Read codes	ICPC
Achalasia	K22.0	530.0	J100.	No code
Balloon dilatation of achalasia			X20Ud	No code
Oesophageal obstruction/stricture/stenosis	K22.2 K31.1 K31.2	530.3	XaB59 J103z XE0aM XaB8i J103z	D84.05 (oesophageal stenosis)
Barrett's esophagus	K22.7	530.85	Xa9Bz X3007	No code
Oesophagitis/Esophagitis	K20	530.1	J101. J101z Xa1q7 X3009	D84.03 (oesophageal reflux with oesophagitis)
Gastro-esophageal reflux disease	K21	530.81	XE0aL XE0aO X3003	D84.00 (oesophageal reflux without oesophagitis)
Esophagic ulcer/perforation/hemorrhage	K22.1 K22.3	530.2 530.4 530.82	J102. J102z	No code
Gastric/duodenal/jejunal/peptic ulcer	K25 K26 K27 K28	531 532 533 534	XE0aP XE0aQ J11y. J11yz	D85.00 D86.00 D86.01
Gastro-intestinal hemorrhage/bleeding	K92.0 K92.1 K92.2 I85.0 I98.21	530.7 530.82 578 456.0 456.1 456.20	J68.. XE0bJ J68zz G850. G8520 XM1RR* XaB3K	D14.00 (haematemesis) D15.00 (melaena) D16.00 (rectal bleeding)
Dysphagia	R13	787.2		D21.00
Diverticulum of oesophagus	K22.5 Q39.6	530.6	PA42. PA45. J106. J106z	D84.01
Gastritis/Duodenitis	K29	535	X301N J155. J15.. J15z. J156. J153. Jyu13 XE2bH J4000 X302J	D87.01

Esophageal surgery	0D11	42	7608.	No code
	0D12		Xa7yZ	
	0D13		X20Tp	
	0D15		Xa3lm	
	0D51		760..	
	0D52		XaB2P	
	0D53			
	0D54			
	0D55			
	0D71			
	0D72			
	0D73			
	0D74			
	0D75			
	0D84			
	0D87			
	0DB1			
	0DB2			
	0DB3			
	0DB4			
	0DB5			
	0DB7			
	0DF5			
	0DH5			
	0DL1			
	0DL2			
	0DL3			
	0DL4			
	0DL5			
	0DM5			
	0DP5			
Hypocalcemia	E83.5	275.41	X40QW	No code

\* "History of". Not to be used for incident diagnoses.

**NOTE:** No codes are available in any of these coding languages for atypical femoral fracture, which is recognized as a precaution of use in the oral bisphosphonates SmPC.

---

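### The second limb of the not-in-first-line outcome is broader than the label restriction: an old reflux or gastritis code counts as compliance, and no planned analysis separates this from real second-line use

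*Protocol*

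**What the plan says.** Section 9.3.2 (New indications of use) makes *not in first line* an either/or outcome. Limb 1 is earlier use of any other anti-osteoporosis drug. Limb 2 needs no earlier drug. It is a "History of any formal contra-indications or precautions for the use of oral bisphosphonates (according to SmPC for alendronic, risedronic and ibandronic acid", with one exclusion and an unlimited look-back: "not recognised as contra-indications or precautions for the use of SR [Appendix 14.3] at any time before SR therapy".

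The codes for limb 2 are in the last table of Appendix 14.3.2. The table does not mark which rows are contraindications and which are precautions, and it sets no limit of severity or recency. Its rows include "Gastro-esophageal reflux disease", "Gastritis/Duodenitis" and dysphagia.

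Section 7.2 gives the restriction that the outcome is meant to measure. It covers patients "for whom treatment with other medicinal products approved for the treatment of osteoporosis is not possible due to, for example, contraindications or intolerance".

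Section 9.7.2.2 (New restrictions) lists "SR use not in first line (as defined above") as one of three primary outcomes. They are analysed by segmented linear regression, separately for incident and prevalent users. Section 9.5.1 plans with 40.4% to 47.9% "for the use of SR as a second line anti-osteoporosis treatment". The sensitivity analyses in section 9.7.5 vary the gap period and the exposure risk window, and leave out Spain. None varies this definition.

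**The concern.** Limb 2 and the restriction are not the same thing. A precaution against a bisphosphonate does not by itself make bisphosphonate treatment impossible. Limb 2 also looks only at oral bisphosphonates, whereas the restriction refers to other approved osteoporosis products in general. A patient whose first osteoporosis drug ever is strontium ranelate is therefore scored as meeting the restriction on the strength of one old gastritis or reflux code.

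At stake is the reading of a primary outcome on the effect of the risk minimization measures. Background gastrointestinal coding sits in the same proportion as real second-line use. A high level, a small change or an apparent improvement could come from either, and the planned analyses cannot tell them apart.

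**Working it through.** **1. The plan's own figure.** For one proportion with 95% confidence and a precision of ±5 points, n = 1.96² × p(1 − p) / 0.05². At p = 0.531 this is 3.8416 × 0.2490 / 0.0025 = 382.7, so 383. This agrees with section 9.5.1: "383 users of SR would suffice to estimate (with 95% confidence and 5% precision) an unchanged prevalence of 53.1% (most conservative scenario"). At p = 0.404 the result is 370, at 0.479 it is 384, and the maximum, at 0.50, is 385. The point made here does not affect the precision calculation.

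**2. Level.** Let P be the share of starters with prior treatment (0.404 to 0.479, section 9.5.1). Let g be the share of never-treated starters with any listed code. The documents do not give g, so it is assumed over a range. The composite reports

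R = P + (1 − P)g.

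For example, 0.404 + 0.596 × 0.20 = 0.523.

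| g (assumed) | R if P = 40.4% | R if P = 47.9% |
|---|---|---|
| 10% | 46.4% | 53.1% |
| 20% | 52.3% | 58.3% |
| 40% | 64.2% | 68.7% |

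Not all of (1 − P)g is error. Some never-treated patients with a listed code could not have taken another product, and section 7.2 admits them. Measured against the restriction, the excess from limb 2 is therefore at most (1 − P)g.

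**3. Change, with g stable.** R₁ − R₀ = (1 − g)(P₁ − P₀). An assumed 20-point rise in prior-treatment share is reported as 18, 16 or 12 points for g = 10, 20 or 40%. As an illustration only, take a plain two-period comparison starting at 40.4%, with 80% power and two-sided 5%. It needs 97 users per period at g = 0, and 119, 146 or 227 at those values of g. The planned analysis is a segmented regression, so these numbers show the direction, not its power.

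**4. Change, with g rising.** With no change in P, the reported share moves by (1 − P)(g₁ − g₀). If g goes from 20% to 30%, that is 0.596 × 0.10 = 6.0 points at P = 40.4%, or 0.521 × 0.10 = 5.2 points at P = 47.9%. With a true 20-point rise from 40.4% and the same rise in g, R goes from 0.523 to 0.604 + 0.396 × 0.30 = 0.723. That is 20.0 points, and the attenuation no longer shows. If g rises to 40%, the reported change is 23.9 points.

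Two routes to a rising g are plausible. The look-back has no limit, so recorded history can lengthen with calendar time. Prescribers may also code such conditions more fully after the two safety communications. The pre-intervention slope in the regression absorbs only a steady drift.

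**5. Errors in the other direction.**
- Table (9.4) 1 shows specialist prescriptions as incomplete in four of the five databases, so prior treatment is missed.
- The exclusion in limb 2 removes conditions that strontium ranelate shares.
- The Dutch coding system has no code for achalasia, Barrett's oesophagus, oesophageal ulcer, oesophageal surgery or hypocalcaemia. Atypical femoral fracture has no code in any system (Appendix 14.3.2).
- Section 9.6.6 treats what is unrecorded as absent.

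These lower the measured compliance by amounts that the protocol does not give.

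**The case against.** The strongest reply is that section 9.3.2 already calls these definitions proxies. It warns of misclassification as well as underestimation, and requires validation or refinement before extraction. The code lists are also reopened for discussion with the partners, and a statistical analysis plan is to follow. A reader might infer that the protocol considers error in one direction only. It does not: misclassification covers both, although underestimation is the only direction named. Even so, nothing commits the study to separating the limbs.

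Second, the label wording is open-ended and mentions intolerance. Databases may not code intolerance, so an upper gastrointestinal history is an arguable stand-in. This stands, and it is a reason to keep limb 2.

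Third, a reader might infer that prior drug use should replace the composite. Section 7.2 does not support that. A never-treated patient with a true contraindication is within the restriction and would be scored as a failure. Prior use also does not prove that other treatment was impossible.

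Fourth, the appendix does not say which rows are contraindications. That has to come from the product information that section 9.3.2 cites, and cannot be settled from the protocol. This stands too.

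**Conclusion.** Limb 2 is broader than the restriction in section 7.2 and tends to overstate compliance. Its size depends on g, which is assumed. Over g = 10 to 40%, limb 2 adds about 5 to 24 points to the prior-treatment share (0.521 × 0.10 to 0.596 × 0.40), and this is an upper limit on its excess over the restriction. If g is stable, a change in prior-treatment share shrinks by the factor 1 − g. If g rises, an apparent improvement can appear without any real one.

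A reader might go further and infer that overall compliance will be overstated and a true effect diluted. The documents do not support that. Errors in the opposite direction exist, g is not given, and dilution requires g to stay constant. Net direction and size cannot be derived. The supported conclusion is that the composite alone cannot be interpreted safely, and that separating its parts is a cheap improvement. The stated sample sizes are unaffected.

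**What to change.** Keep the composite as defined and add the following.

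1. In section 9.7.2.2, also report and run the interrupted time series separately for (a) previous use of another anti-osteoporosis drug and (b) limb 2 among patients without such use.
2. In the last table of Appendix 14.3.2, flag each row as contraindication or precaution according to the product information that section 9.3.2 already cites.
3. In section 9.7.5, add a sensitivity analysis of the composite that drops patients who qualify only through a precaution from the numerator.
4. In section 9.3.2, state that this proxy can also overestimate compliance.

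The cost is one extra column in the code table and a few extra series from data that are extracted anyway. The compliance figure may turn out less favourable.

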### 9.6.6. Missing data

Since the underlying data represent attended medical care we assume that absence of information of clinical events means absence of that condition. Lack of information on smoking, and alcohol use may occur, but this is unlikely differential.

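### The severe-osteoporosis series depends on how completely BMD and weight are recorded, so on its own it cannot separate a change in prescribing from a change in recording

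*Protocol*

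**What the plan says.** Section 9.3.2 (New indications of use) defines severe osteoporosis by two limbs joined by OR. The first is "History of a previous osteoporotic fracture" at any time before SR initiation. The second is a value of at least 10% for "5-year fracture risk according to the Garvan prediction tool", limited to cases "where data on age and either bone mineral density or weight are available for the estimation of risk". No date is set for the Garvan inputs.

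Section 9.7.2.2 (New restrictions) makes this the first of three outcomes: "Primary outcomes of interest will be proportion of SR users with" a prior fracture or a high estimated risk. The denominator is not limited to users whose risk can be computed. The series is monthly, is analysed by segmented linear regression in each database, and is run separately for incident and prevalent users. Each database serves as its own control. Section 9.7.4 then pools all estimates across databases.

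On data quality, 9.3.2 warns that "operational definitions are proposed using some proxies which could lead to some misclassification or underestimation of the new restrictions" and foresees refinement with the partners before extraction. Section 9.9 (Information bias) repeats the warning and mentions BMD. Section 9.6.6 states that "absence of information of clinical events means absence of that condition".

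**The concern.** A fracture-free user with no weight or BMD on file stays in the denominator but has no route into the numerator. Two users with the same true risk can therefore be classified differently because only one was measured.

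This has two consequences. First, the outcome can mean different things by source. Section 9.4.5 lists weight among the SIDIAP variables, while the description of the Aarhus data in 9.4.4 lists neither weight nor BMD. Pooling would then combine a fracture-only proportion with a fracture-or-Garvan proportion under one label. Second, a recording deficit that stays constant largely cancels in a before/after comparison within a source, but one that changes at the intervention does not. It would appear as a change in level or slope, which is what the analysis tests. The protocol's warnings concern misclassification and underestimation in general. They do not address recording that changes over time.

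**Working it through.** **The plan's own figure.** Section 9.5.1 sizes this outcome on prior fracture, with prevalence from 13.0% to 53.1%. For 95% confidence and ±5 points, n = 1.96² × 0.531 × 0.469 / 0.05² = 382.7, so 383, as stated. No stated figure is wrong.

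**Model.**
- f = share with a prior fracture: 13.0% or 53.1% (9.5.1).
- q = share of fracture-free users whose true Garvan risk is at least 10%: not in the documents, assumed 30% to 70%.
- a = share of those high-risk, fracture-free users with BMD or weight recorded: not in the documents, assumed.

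If users without inputs count as not severe, the observed proportion is P = f + (1 − f)·q·a.

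**Differences in level.** The shortfall against full recording is (1 − f)·q·(1 − a). At a = 50%:
- smallest: 0.469 × 0.30 × 0.50 = 7.0 points
- largest: 0.87 × 0.70 × 0.50 = 30.5 points

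The same figures give the gap between a source with no inputs (a = 0) and one with inputs for half, for identical patients.

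**Change in recording, same patients.** The shift is (1 − f)·q·(a₁ − a₀). For a 10-point change:
- f = 53.1%: 0.469 × 0.30 × 0.10 = 1.4 points, to 0.469 × 0.70 × 0.10 = 3.3 points
- f = 13.0%: 0.87 × 0.30 × 0.10 = 2.6 points, to 0.87 × 0.70 × 0.10 = 6.1 points

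If a₁ = a₀, the shift is zero. If recording falls, the sign reverses.

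**Change in recording that matches the planned 5-point precision:** 0.05 / [(1 − f)·q].
- f = 13.0%: 0.05/(0.87 × 0.70) = 8 points, to 0.05/(0.87 × 0.30) = 19 points
- f = 53.1%: 0.05/(0.469 × 0.70) = 15 points, to 0.05/(0.469 × 0.30) = 36 points

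**What segmented regression does with it.** This was simulated with no change in patients, q = 40%, and a step in recording at the start of the assessment period. There were 60 months before, a 10-month lag left out of the fit, 20 months after, independent months and 1,000 runs. All of these settings are assumptions.

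| f | Recording | Mean false level change (50 / 200 users per month) | Significant at 5% (50 / 200 users per month) |
|---|---|---|---|
| 13.0% | 30% → 30% | about 0 | 5.4% / 4.4% |
| 13.0% | 30% → 40% | 3.5 / 3.6 points | 19.5% / 55.9% |
| 13.0% | 30% → 60% | 10.4 / 10.5 points | 85.1% / 100% |
| 53.1% | 30% → 30% | about 0 | 4.7% / 5.0% |
| 53.1% | 30% → 40% | 1.8 / 1.9 points | 7.1% / 16.2% |
| 53.1% | 30% → 60% | 5.5 / 5.6 points | 29.4% / 85.3% |

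**The case against.** A reader might infer that the protocol orders unmeasured users to be scored as not severe. It does not say so. The scoring is implied by the OR definition and the unrestricted denominator. Section 9.6.6 adds little, because its rule covers clinical events, whereas weight and BMD are measurements. Users with a recorded fracture are unaffected whether or not they were measured.

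A reader might also infer that recording will rise after the DHPCs and make the measures look successful. The documents do not support that. They give no recording rates, and the communications they describe restrict who may be treated; they are not described as asking for measurement. The direction is open too. Sections 6 and 9.3.2 say GPs may no longer initiate SR in Italy or Spain, and Table (9.4) 1 marks specialist prescriptions as incomplete in four of the five sources. Care moving to specialists could lower what GP records capture.

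The design gives some protection. Segmented regression controls for baseline level and trend, so steady improvement in recording is largely absorbed and only a break near the DHPCs remains. A source with no inputs throughout has no time-varying artefact of this kind. The protocol also concedes underestimation, plans refinement before extraction, and defers detail to a statistical analysis plan.

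These points remove any claim that bias is present or that its direction is known. They do not remove the dependence on recording, because the definition and the denominator are set in the protocol. The planned refinement does not commit to tracking completeness over time.

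**Conclusion.** The point holds in a limited, conditional form. As defined, the severe-osteoporosis outcome mixes severity with completeness of BMD and weight recording, differs in meaning between sources that are later pooled, and cannot alone separate a change in prescribing from a break in recording. The illustrated shift of 1.4 to 6.1 points per 10-point change in recording rests on q of 30-70%, on f of 13.0% to 53.1% from 9.5.1, and on unassessable users counting as not severe. It affects one of the three restriction outcomes. That is enough to justify an inexpensive safeguard, but not to call the planned analysis invalid.

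**What to change.** In 9.7.2.2:

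1. Add an interrupted time series for prior fracture alone in all SR users, beside the composite. This is the quantity that 9.5.1 sizes and that 9.3.4 treats as the proxy for severity.
2. Report, by month and database, the share of users with Garvan inputs recorded before SR start.
3. Show users with neither a fracture nor inputs as not assessable rather than not severe.
4. Use one set of Garvan inputs (BMD or weight) consistently within each database.
5. Treat a series among users with a fracture or recorded inputs as a sensitivity analysis only. Its denominator may itself change in composition if the DHPCs alter who is measured. Users with a fracture but no inputs should stay in it, since their status is known.

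The cost is one or two extra series and a completeness table, and the sensitivity analysis has a smaller denominator. In a source without weight or BMD, only the fracture series is informative.
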